The original Bränemark protocol dictated that the initial phase of implant osseointegration should be at least 4-6 months before any prosthetic restoration is placed (Bränemark, 1983). However, technological advancements have resulted in modern dental implant protocols that provide the possibility to immediately load implants, with the advantage of reducing the length of treatment time and satisfying patient demands (Chung, 2011). In addition, this protocol avoids the recourse of a removable prosthetic whose placement may interfere with healing (Collaert, et al., 2008). In numerous clinical trials, immediate loading has been shown to have excellent survivability and now is deemed a reliable treatment option for edentulism in the mandible, with an overall survival rate greater than 98% (Chiapasco, 2004), both for fixed or removable full restorations. The reported success in immediate loading in the mandible has encouraged the application of a similar treatment in the maxilla. Compared to the mandible, the main factor which has been considered to jeopardize the success for maxillary overdentures is related mainly to poorer bone density (Nordin, et al., 2007). Lekholm and Zarb described maxillary bone as more trabecular and softer in nature (type 3 or type 4), whereas mandibular bone is more cancellous and denser (type 1 or type 2) (Lekholm, et al., 1985). This anatomic difference results in lower primary stability and, in case of immediate loading, may expose the implants to the risk of excessive micromotions (Trisi, et al., 2009) (Javed, et al., 2013): if the implant undergoes micromovements exceeding 150 μm , new bone formation will be prevented and a non-calcified, collagenous poorly vascularized scar tissue will characterize the interface (Brunski, et al., 1979) (Szmukler-Moncler, et al., 2000).

Consequently, these factors advise the use of moderately rough surfaced implants ($\text{Sa} = 1.0\text{-}2.0 \mu\text{m}$), which lead to higher bone-to-implant contact and higher removal torque values compared to conventional machined surfaces

WVU+kc Protocol #: 1801929813

PI: [name]

Approved:15-Dec-2021Expires:14-Dec-2022Number:1801929813

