Primary Objective – The primary objective of this study is to evaluate radiographically at 6 and 12 months post-loading the performance of the Roxolid™ BLX 3.75 mm implants placed using a flapless guided surgery and immediately loaded with a maxillary overdenture. The outcome will be evaluated using peri-implant, radiographic bone level changes from baseline to 6 and 12 months post implant placement.

Secondary Objective(s) – The secondary objectives include evaluation of:

- Condition of the peri-implant mucosa (pocket depth and bleeding on probing).
- Implant stability quotient (ISQ) at baseline and 12 months
- Implant survival at 6 months and 1 year
- The nature and the frequency of surgical and prosthetic complications
- Patient-centred outcomes (OHIP 14)
- Accuracy of the implant placement (additional CBCT is required)

Study Design & Methodology

General overview

This study will be performed at the WVU School of Dentistry. Total number of patients is from a minimum of 15/20 subjects. Each subject will receive 4 implants. Implants will be placed flapless using a guided surgical protocol and will be immediately loaded by means of a locator retained maxillary overdenture. The study is an Investigator Initiated Project: Straumann accepted to partly sponsor the study, providing some financial support and materials (implants and abutments). Also, study participants will receive \$100 as reimbursement for travel expenses for each of the 3 months, 6 months and 12 months recall visits, (visit 6,7, and 8 as per visit schema) for a total of \$300 .

Pre-treatment procedures

An initial evaluation will be conducted to determine whether a patient meets the study inclusion criteria. This evaluation will include medical history, clinical examination and radiographic examination (OPT). A pre-operative prosthetic evaluation of the existing prostheses will be made to establish their quality and the need for a new set of complete dentures before the implant placement. The maxillary denture will be used as radiographic guide for the pre-treatment CBCT assessment. The tridimensional image obtained with the CBCT will be used for the surgical planning of the implant positioning by means of a dedicated implant planning software (coDiagnostix, Dental Wings Gbmh, Chemniz Germany)) and a stereo-lithographic surgical guide will obtained.

Surgical procedures

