Patients will be recalled at 1, 2, 4, 12 weeks and 6 months and 12 months after surgery. At the post-operative visit occlusion will be checked, as well as stability and retention of the prostheses and the need for any prosthetic maintenance. Periapical radiographs will be taken at baseline and 6 and 12 months visit by paralleling technique using a Rinn® (Dentsply Rinn, Elgin, Illinois, USA) film holder. The film holder will be indexed on the Locator attachment so that the film position could be reproduced for the follow up radiographs. All patient complaints or any complications resulting from a change in health status from baseline or any implant related complications such as pain, paresthesia or peri-implant infection will be recorded as an adverse event in the CRF and will be monitored until the condition is resolved. OHIP-14 questionnaire will be administered at baseline, at 2 weeks' post-surgery and at 3 months, 6 months and 1 year.

Outcome variables

The following clinical parameters will be considered for treatment evaluation:

Independent Variables

- Patient age
- Patient gender
- Implant length
- Implant position
- Implant insertion torque

Dependent Variables:

- Implant failure/success
- Radiographic bone level change
- Prosthetic complications
- Patient-centered outcomes
- PD
- BoP
- PI (O'Leary 1974)
- KT
- (ISQ analysis)

Implant Failure/Success

The success criteria for the implants will be 1) no radiolucency around the implant, 2) no mobility, 3) no suppuration, pain or ongoing pathologic process. Implant that will not fulfil the success criteria will be considered as failed. The failed implants will be removed and replaced with another implant after 8 weeks of healing of the implant site. The replaced implant will be loaded after 3 months of healing.

Radiographic bone level

Radiographic bone level (RBL) change will be measured on standardized periapical radiographs. A masked examiner will make the bone height measurements. The distance between the implant platform and the most coronal level of the

WVU+kc Protocol #: 1801929813

PI: [name]

Approved:15-Dec-2021Expires:14-Dec-2022Number:1801929813

bone deemed to be in contact with the implant surface will be evaluated. Mesial and distal bone height measurements will be averaged for each implant. The measurements of the bone level at implant placement will be considered as baseline. The RBL change will be calculated in comparison with the baseline value.

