Prosthetic complications

The number and nature of prosthetic complications will be recorded as well as the number and nature of any unplanned visit for each group.

Patient-centered outcomes

Patient centered outcomes will be recorded through the Oral Health Impact Profile (OHIP-14), which is a 14-items questionnaire designed to measure self-reported functional limitation, discomfort and disability attributed to oral conditions (Slade 1997). The OHIP-14 has been shown to be reliable (Slade 1997); sensitive to changes (Locker, Jokovic e Clarke 2004) and it has adequate cross-cultural consistency (Allison, et al. 1999).

Accuracy of the guided system

The Software will compare the actual position of the implants with the pre-surgical planned placement. Difference in angulation and depth will be recorded. A second CBCT will be performed immediately after the surgical placement of the implants.

Target Population & Recruitment Methods

The study population consists of 15-40 patients (15 minimum, 40 maximum), male or female ≥ 21 years of age, requiring 4 implants supported maxillary overdenture. The enrollment of patients will be open to a diverse racial and ethnical backgrounds in order to ensure equitable selection.

Inclusion Criteria – Inclusion criteria include:

- Males and females must be at least ≥ 21 years of age
- Fully edentulous maxilla
- The implant site has to be healed for at least 4 months after extraction
- Wearing complete dentures deemed adequate
- Orthopantomogram available (OPT)
- Adequate amount of bone at least at the 2nd premolar position to house a 3.75 x 10 mm implant
- No bone grafting required
- Implant IT ≥ 20 N/cm

Exclusion Criteria – These are both systemic and local exclusion criteria:

Systemic exclusion criteria

- Conditions requiring chronic routine prophylactic use of antibiotics
- Conditions requiring prolonged use of steroids
- History of leukocyte dysfunction and deficiencies
- Bleeding disorders
- History of neoplastic disease requiring use of radiation or chemotherapy
- Metabolic bone disorders
- Uncontrolled endocrine disorder
- Use of any investigational drug or device within the 30-day period prior to implant surgery
- Smoking more than 10 cigarettes a day
- Alcoholism or drug abuse
- Patient infected with HIV

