Risk – The risks for the participants are represented by the possible complications from the surgical procedure, which may include: implant failure, pain; postoperative discomfort; swelling; restricted mouth opening that may last for several days; bleeding; infection requiring additional treatment; stretching of the corners of the mouth resulting in cracking and/or bruising; change in the occlusion (bite); jaw joint pain; fracture of the jaw; injury to nerve branches; numbness or tingling of the lip, gums, cheek that may last for several months.

Benefit – The advantages of implant rehabilitations for the patients include: improved stability and retention of denture; increased masticatory efficiency; slower rate of bone ridge resorption. In particular, according to a recent prospective study, patient satisfaction significantly increased for implant-supported maxillary dentures compared with old dentures in all seven OHIP parameters (functional limitation, physical pain, psychological discomfort, physical disability, psychological disability, social disability, handicap), as well as for cleaning ability, general satisfaction, ability to speak, comfort, esthetics, and stability (Zembic, Wismeijer 2014). The single patient may not receive any direct benefit from this study. The knowledge gained from this study may eventually benefit others.

Statistical Analysis Plan

Primary outcome variables will test for normal distribution and two-way Paired t test or Student t-test will be used to compare the means. Descriptive statistics will be used to describe patient population. Non-parametric inferential

statics will be used for ordinal/non-parametric data set. The chosen sample size will provide enough power to deliver significant results.

Data Safety Monitoring – Any information that is obtained as a result of this research will be kept as confidential as legally possible. The research records and test results may be subpoenaed by court order or may be inspected by the study sponsor or federal regulatory authorities without your additional consent. In any publications that result from this research, neither name nor any information from which the patients might be identified will be published without their consent.

Safety Monitoring & Unanticipated Event Reporting

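### Five explanatory factors are listed with no analysis assigned and no allowance for four implants per patient; tests that treat implants as independent would have wrong error rates

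*Combined protocol and SAP*

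**What the plan says.** The Outcome variables section introduces its lists with "The following clinical parameters will be considered for treatment evaluation". The independent variables are patient age, "Patient gender", "Implant length", "Implant position" and insertion torque. Nine dependent variables follow, among them radiographic bone level change.

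The Statistical Analysis Plan says that, for the primary outcome variables after a check of normality, "two-way Paired t test or Student t-test will be used to compare the means". It adds descriptive statistics for the population and unnamed non-parametric inference for ordinal or non-parametric data. No regression or mixed model appears, and no test is tied to any of the five factors. The null hypothesis concerns change between baseline, 6 and 12 months only.

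Three further facts matter:

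- General overview: "Each subject will receive 4 implants". With the 15 to 40 patients given under Target Population, that is 60 to 160 implants.
- Radiographic bone level: mesial and distal readings are averaged to one value per implant. No step averages to the patient.
- Surgical procedures: torque is recorded in four ordered categories (20, 30, 40, 50 N/cm), and a patient with torque below 20 N/cm leaves the study.

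**The concern.** The study has one arm. A paired t-test covers change over time, but a two-sample Student t-test needs two groups, and the listed factors are the natural source of them. The outcome is stored per implant, so the analysis most easily run on that dataset compares implants with implants as if each came from a different person.

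Implants in one mouth share bone quality, hygiene, denture and bite, so their bone-level changes are likely to be correlated. Age and gender are constant within a mouth. Position varies mainly within it. Length and torque can vary both ways. One independent-units test cannot be right for all of these. Age and torque also do not fit a two-group test without cut-points, and none is given.

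The factors bear on the study's rationale. The Background says of maxillary compared with mandibular bone that "This anatomic difference results in lower primary stability", with excess micromotion as the risk under immediate loading. A reader of the final report will look at torque in particular.

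**Working it through.** **Inputs from the documents.** Four implants per patient; 15 to 40 patients; one outcome value per implant per visit. The plan gives no alpha, power, effect size, standard deviation or ICC, so it has no figure to reproduce.

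**Assumptions.** Two-sided alpha 0.05; normal outcome with equal correlation (ICC) between a patient's implants; ICC 0.1 to 0.5; patients divided as evenly as possible for a patient-level factor; two implants in each class for position (the protocol defines no position classes).

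**Variance of the difference, relative to what the implant-level t-test assumes**

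- Patient-level factor: 1 + (4 − 1) × ICC = 1 + 3 × ICC.
- Factor split 2/2 in every mouth: 1 − ICC.

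The large-sample type I error is 2 × [1 − Φ(1.96 / √ratio)]. At ICC 0.5:

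- Gender: ratio 2.5; 1.96 / 1.581 = 1.24; error 0.215.
- 2/2 position: ratio 0.5; 1.96 / 0.707 = 2.77; error 0.0056.

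**Type I error with 20 patients** (20,000 simulated trials per cell; large-sample value in brackets)

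| ICC | Gender | Position, 2/2 split |
|---|---|---|
| 0.1 | 0.084 (0.086) | 0.038 (0.039) |
| 0.2 | 0.124 (0.121) | 0.029 (0.028) |
| 0.3 | 0.161 (0.155) | 0.021 (0.019) |
| 0.5 | 0.223 (0.215) | 0.008 (0.006) |

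Results at 15 and 40 patients are close to these. At ICC 0.5, gender is 0.216 to 0.224 and position 0.006 to 0.008 over the three sizes. At ICC 0 both are about 0.05. Analysed at the right level (patient means for gender, a within-patient contrast for position), the error is 0.047 to 0.052 throughout.

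**Length and torque.** These were simulated as a two-class factor with its own within-patient correlation of 0, 0.3, 0.6 or 0.9. At outcome ICC 0.5 and 20 patients, the type I error is 0.051, 0.086, 0.121 and 0.182: about nominal if the factor does not cluster by patient, and increasingly liberal if it does.

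**Power for a 2/2 factor, assumed effect 0.5 SD** (10,000 trials per cell)

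| Patients | ICC | Implant-level t-test | Within-patient contrast |
|---|---|---|---|
| 15 | 0.1 | 0.48 | 0.48 |
| 15 | 0.3 | 0.48 | 0.58 |
| 15 | 0.5 | 0.48 | 0.72 |
| 40 | 0.1 | 0.90 | 0.90 |
| 40 | 0.3 | 0.92 | 0.96 |
| 40 | 0.5 | 0.95 | 0.99 |

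**Is a random patient effect enough?** Not if both visits enter one model. Each implant then gives two changes that share a baseline. Let ρ be the correlation of an implant's two residuals after removing the patient effect. For a 2/2 factor the variance of the contrast is multiplied by 1 + ρ, while the fitted residual variance shrinks to (7 − ρ)/7 of its true value, because each patient gives eight values and so seven within-patient degrees of freedom. The ratio is (1 + ρ) / [(7 − ρ)/7].

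- ρ = 0.2: 1.2 / 0.971 = 1.235; 1.96 / 1.111 = 1.76; error about 8%.
- ρ = 0.8: 1.8 / 0.886 = 2.03; 1.96 / 1.425 = 1.375; error about 17%.

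Simulation gave the same range. The model therefore needs an implant-level term, or must take one visit at a time.

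**The case against.** The strongest reply is that this criticises a method the plan never states. The t-tests are assigned to the primary outcome variables, the null hypothesis is about time, and no primary or secondary objective names the five factors. They might be meant for description only. This stands: the error rates are conditional on a reading. It does not remove the gap, because the factors are called independent variables, the outcome is held per implant, and nothing in the plan says which unit will be analysed.

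It can also be said that torque, being ordinal, could fall under the non-parametric sentence. That too is fair, and a reader who infers that the plan can do nothing but compare means goes too far. But those methods are unnamed and not linked to the factors, and ordinary rank tests for independent samples make the same independence assumption.

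A reader might infer that implant-level factors as a class err in the opposite direction to patient-level ones. The documents do not support that. It holds for a factor balanced within each mouth; length and torque may err in the same direction as gender or hardly at all.

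A reader might also infer that a real position effect will probably be missed and a false gender effect probably found. Neither follows. At 40 patients the implant-level test has power of about 0.90 to 0.95 for the assumed effect, and at ICC 0.1 there is practically no loss even with 15. A false-positive rate of 9% to 22% is inflated, but it is not a likely event. Nor does the Background contrast anterior with posterior maxilla; it contrasts maxilla with mandible.

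**Conclusion.** The point holds in a limited form. The plan lists five explanatory factors, gives no method for relating them to bone-level change, and ignores the grouping of four implants within a patient. If implants are analysed as independent, which is inferred rather than stated, then with 20 patients and an assumed ICC of 0.1 to 0.5:

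- a patient-level factor such as gender is tested at a true level of about 9% to 22%;
- a factor split 2/2 within each mouth is tested at about 4% down to 0.7%, with a power loss that is material only at small enrolment and higher ICC;
- length and torque lie between about nominal and clearly too liberal, according to how strongly they cluster by patient.

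All of this vanishes at ICC 0, and the documents give no ICC. The comparison over time in the null hypothesis does not use these factors, so this is a correction to the explanatory analysis. It is worth making before the data are analysed.

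**What to change.** In the Statistical Analysis Plan, state that the five factors are examined by one linear mixed model for radiographic bone level change, labelled exploratory, in place of any t-test or rank test on implants. Specify:

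- a random patient effect and an implant-within-patient effect with visit as a fixed effect; or, more simply, the 6-month and 12-month changes analysed separately with a random patient effect;
- a small-sample degrees-of-freedom correction (Kenward-Roger or Satterthwaite);
- torque and length each entered as the patient mean and the implant's deviation from it, so that between-patient and within-patient associations are not mixed;
- the classes used for position and the coding of the torque categories, fixed in advance, with age kept continuous;
- estimates with 95% confidence intervals as the main report;
- an order of priority among the factors, so that their number can be limited to what the enrolled patients support;
- a statement that torque is observed only at or above the 20 N/cm entry limit, so its slope applies to that range.

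The cost is SAP wording and standard software, with no new data or visits. The drawback is that age and gender, which rest on 15 to 40 patients and not 60 to 160 implants, will be estimated imprecisely and must be presented that way.

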The implants will be inserted under local anesthesia, following consumption of prophylactic antibiotic medications consisting of 2 grams of amoxicillin 1 hour before the surgical procedure. If the patient is allergic to penicillin or penicillin derivatives, clindamycin or other classes of antibiotics will be administered according to ADA guidelines. The implant placement will be performed using the stereo-lithographic surgical guide with a flapless approach, that is no crestal incision and flap elevation is needed. The osteotomy site will be prepared following the drilling sequence provided by the manufacturer surgical manual. The implant will be placed and the maximum value of insertion torque (peak of insertion torque, IT) will be measured during the seating of the most coronal implant threads by means of the surgical unit (W&H, Burmoos, Austria) and recorded as 20, 30, 40, 50 N/cm IT category. In case of IT lower than 20 N/cm the implant will not be immediately loaded; the patient will be excluded from the study and the implant treatment will be completed following the standard delayed protocol. Novaloc TiN abutments will be secured on the implant at 10 N/cm torque.

Prosthetic procedures

The denture will be immediately connected to the implants. The Novaloc TiN cap attachments will be picked up intra-orally using cold curing resin. To avoid contact of the resin with the surgical wound, a circular portion of a sterile rubber dam sheet will be adapted on the cap attachment once placed on the Locator abutment during the pickup procedure. Occlusion is then checked and adjusted if necessary as well as the adaptation on the residual ridges and the patient dismissed. As post-surgical instructions, the patients will be asked not to brush the operated areas and to rinse instead with 0,12% chlorhexidine solution twice a day for 1 minute for 14 days. Pain control is provided with 400 mg ibuprofen, as needed. Soft diet is recommended for 2 weeks. The patients will be instructed not to remove the prosthesis for one week.

Follow-up visits

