The safety of participants will be monitored during the study by the PI and Co-Is. All the Co-Is will report to the PI. At each visit, the presence of adverse events and unanticipated events will be evaluated and promptly reported to the PI and to the IRB.

Study Duration & Timeline

	Visit 1 Screening and pre-surgical planning	Visit 2 Implant Placement	Visit 3 1 week FU	Visit 4 2 weeks FU	Visit 5 4 weeks FU	Visit 6 3 months FU	Visit 7 6 months FU	Visit 8 12 months FU	
Visit Window			IP + 1w	IP + 2w	IP + 4w	IP + 12w (± 7d)	IP + 24w (± 7d)	IP + 12m (± 1m)	
Informed consent	X								
Subject demographics	X								
Medical/Surgical history	X								
Inclusion/Exclusion criteria	X								
Oral examination	X								
Denture assessment	X								
CBCT	X	X							
Radiographic examination (PA)		X					X	X	
Prosthesis connection		X							
Implant data IT, length Condition of periimplant		X			X	X	X	X	
Soft tissue condition: KG Plaque	X	X			X	X	X	X	
AE/ADE		X	X	X	X	X	X	X	
Implant stability (ISQ)		X				X	X	X	
OHIP14	X			X		X	X	X	
Clinical photography	X	X	X	X	X	X	X	X	

Section III: Informed Consent Process

Protected Health Information (PHI)

The patients' PHI will include:

1. **Names**
2. **All geographical information** – this includes street address, city, county, precinct, ZIP code, and their equivalent geocodes.
3. **All elements of dates** – this includes dates directly related to an individual, including birth date, admission date, discharge date, date of death.
4. **Phone and Fax number(s)**
5. **Electronic mail (E-mail) addresses**

Informed Consent Process

The informed consent will be given to the patient first screening visit. The patient will be given the opportunity to ask questions about the research and to receive answers about areas the patient does not understand. The patient will be asked to read the informed consent document carefully and, if necessary, to discuss about the research with family members, primary care physicians or friends before making a decision.

Confidentiality & Privacy

Confidentiality – All data collected will be kept for a minimum of 3 years after the conclusion of the research project. Physical copies of data collected will be locked in a drawer or file cabinet, within a locked room or office. Digital data will be on a password protected database. All participant identifiers will be stored separately from the data collected.

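### The primary bone-level rule has no step scaling each film to a known dimension, so magnification differences that remain after film standardisation stay uncorrected in the bone-level change

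*Combined protocol and SAP*

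**What the plan says.** The Primary Objective makes bone-level change the primary outcome: "The outcome will be evaluated using peri-implant, radiographic bone level changes from baseline to 6 and 12 months post implant placement".

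The measurement rule is in Outcome variables, under Radiographic bone level. The films are described as standardised: "Radiographic bone level (RBL) change will be measured on standardized periapical radiographs". A masked examiner measures "The distance between the implant platform and the most coronal level of the" bone judged to touch the implant. Then "Mesial and distal bone height measurements will be averaged for each implant", and "The RBL change will be calculated in comparison with the baseline value", baseline being the film at implant placement.

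Film geometry is dealt with under Follow-up visits. Films at baseline, 6 and 12 months use the paralleling technique with a Rinn holder. For repositioning, "The film holder will be indexed on the Locator attachment".

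Two other places bear on the point. The visit table under Study Duration & Timeline collects "Implant data IT, length" at the placement visit, but Outcome variables uses implant length only as an independent variable. Surgical procedures states that "Novaloc TiN abutments will be secured on the implant at 10 N/cm torque", and the Study Design paragraph at the front of the protocol also names Novaloc.

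**The concern.** A distance read from a film is the true distance multiplied by that film's magnification. When two films are subtracted, a difference in magnification acts on the whole platform-to-bone distance, not only on the part that changed, and so can look like bone loss or gain. Averaging mesial and distal does not help, because both sides of one film share the same magnification. Masking the examiner addresses expectation, not geometry.

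The stated null hypothesis compares baseline with 6 and 12 months in one treated group. There is no control arm in which a shared projection difference would cancel. The plan positions the films carefully, but it describes no check that positioning succeeded, no rule for a film where it did not, and no correction for what remains. Every film contains an object of recorded length that could supply that correction.

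**Working it through.** The documents give no magnification, baseline distance, expected change, standard deviation or measurement error for bone level. There is no stated figure to reproduce, and all numerical inputs below are assumptions except the 3.75 mm implant diameter (Primary Objective).

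**Formula.** Let d0 and d1 be the true distances at baseline and follow-up, and m0 and m1 the relative magnification errors of the two films.

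- Observed change = (1 + m1) × d1 − (1 + m0) × d0
- Error = m1 × d1 − m0 × d0 = m1 × (d1 − d0) + d0 × (m1 − m0)

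**Mismatch on the follow-up film** (m0 = 0, so error = m1 × d1):

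| d0 to d1 (mm) | True change (mm) | Error at 5% (mm) | Error at 10% (mm) |
|---|---|---|---|
| 0 to 0.3 | 0.3 | 0.015 | 0.03 |
| 0 to 0.6 | 0.6 | 0.03 | 0.06 |
| 0.5 to 1.0 | 0.5 | 0.05 | 0.10 |
| 2.0 to 2.5 | 0.5 | 0.125 | 0.25 |

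Relative to the true change this is 5-10% in the first two rows, 10-20% in the third (0.05/0.5 to 0.10/0.5) and 25-50% in the fourth (0.125/0.5 to 0.25/0.5). The result depends heavily on d0. With d0 = 0 the term d0 × (m1 − m0) vanishes.

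**Mismatch on the baseline film** (m1 = 0, so error = −m0 × d0). The sign reverses: −0.025 to −0.05 mm for 0.5 to 1.0 mm, and −0.10 to −0.20 mm for 2.0 to 2.5 mm. Loss can be hidden as well as created.

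**Equal magnification on both films**, which is what the indexed holder aims for. The error is only proportional: on a 0.5 mm change, 0.05 × 0.5 = 0.025 mm or 0.10 × 0.5 = 0.05 mm.

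**Random mismatch.** If the two films' errors are independent with SD 5% or 10%, and the small term in the change itself is ignored, the added SD per implant is d0 × SD(m) × √2. That is 0.071 or 0.141 mm at d0 = 1 mm, and at most 0.283 mm at d0 = 2 mm. Against an assumed SD of change of 0.5 mm, √(0.5² + 0.071²) = 0.505, √(0.5² + 0.141²) = 0.520 and √(0.5² + 0.283²) = 0.575. Intervals are wider by about 1%, 4% and 15%. If the errors correlate at 0.8, because the same holder is used, 0.071 mm falls to 0.05 × √(2 × 0.2) = 0.032 mm.

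**What scaling removes.** Multiplying by true over measured implant length brings m0 and m1 to zero, apart from reading error, and removes foreshortening along the implant axis. Foreshortening is small anyway: 1 − cos(angle) is 0.4% at 5 degrees and 1.5% at 10 degrees, or 0.006 and 0.023 mm on a 1.5 mm distance.

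**What scaling does not remove.** Bone lying one implant radius (3.75/2 = 1.875 mm) from the axis shifts on the film by up to 1.875 × tan(angle) if the beam angle changes: about 0.07 mm at 2 degrees, 0.16 mm at 5 degrees and 0.33 mm at 10 degrees (assumed angles). Only reproducible film geometry limits this.

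**The case against.** The strongest reply is that the plan already controls projection. The paralleling technique, a Rinn holder and an indexed position are specified for every time point, so only a residual reaches the outcome. This stands, and it limits the point to that residual. A reader might infer that the indexed holder is the sole safeguard, or that magnification and angulation differences enter the outcome in full. The text supports neither.

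A reader might also infer that the plan prescribes raw, unscaled distances. It does not: it is silent on how film distances become millimetres, so the supportable statement is that no scaling step is described. The silence still matters for a primary outcome, because it leaves the method open until after the films have been seen.

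A third inference is a systematic difference between surgery-day and recall films that biases the mean. The documents show no mechanism for one, since technique and holder are the same throughout. It is a possibility that this design could not cancel, not a demonstrated bias.

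Finally, the Locator and Novaloc wording might be read as showing that standardisation fails. General overview and Prosthetic procedures also use the Locator name, so this is a naming inconsistency, and nothing says the holder cannot be indexed on the part fitted.

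It is also fair that scaling adds a reading error of its own and needs the implant's full length on the film, which the documents do not guarantee. The added error should be small: for a 10 mm implant (the size named in the inclusion criteria), misreading the length by e mm alters a 1.0 mm distance by about e/10 mm.

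**Conclusion.** The point holds in a limited form. Film geometry is standardised in advance, but the rule for the primary outcome describes no step that removes residual magnification differences, although the length needed to do so is already collected.

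The effect in this trial cannot be determined from the documents. Under an assumed 5-10% mismatch on the follow-up film it runs from about 0.015-0.06 mm with a baseline distance near 0, through 0.05-0.10 mm for 0.5 to 1.0 mm, to 0.125-0.25 mm for 2.0 to 2.5 mm. If the holder keeps magnification equal, it is no more than 0.025-0.05 mm on a 0.5 mm change at 5-10%. A purely random residual would cost little precision except at large baseline distances, and would partly average out over at least 60 implants (15 patients × 4). Any systematic part would not average out.

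This is an inexpensive improvement to the primary measurement, not a defect that invalidates it. It deals with magnification and axial foreshortening only; parallax may be as large or larger and remains a matter of film positioning.

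**What to change.** Add to the Radiographic bone level definition that, on every film, the same masked examiner measures each implant's length and multiplies the mesial and distal distances by recorded length divided by measured length before averaging. Where the apex is not visible, name another known implant dimension as the reference. One along the implant axis is preferable, because a width does not register axial foreshortening.

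State beside it that scaling does not correct parallax. Give a rule for visibly distorted films and a repeat-reading check, so that the remaining error is known.

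Separately, reconcile the Locator wording for the film-holder index in Follow-up visits with the Novaloc components named in Study Design and Surgical procedures.

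The cost of scaling is one extra on-screen measurement per implant per film and its small reading error. It needs no new exposure, visit or staff, and it can be applied to stored films. Repeat reading of a subset adds some examiner time.
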